#### Baseline and day 90 post stem cell infusion

Pulmonary function test

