## Baseline and day-90 post infusion

Pulmonary function test

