## 9 STATISTICAL CONSIDERATIONS

Statistical analyses will be descriptive. Summary statistics will consist of sample size (N), means, standard deviations, medians, and minimum and maximum values for continuous variables, and counts and percentages for categorical variables. Tables will summarize all safety and efficacy outcome measures by actual treatment received. Summary tables will indicate the number of subjects with complete data for each measurement, event or outcome. No substitutions will be made for missing data. All analyses will be based on available data.

A detailed Statistical Analysis Plan will be written prior to data analysis. Significant deviations from the original statistical analysis plan will be detailed in the final study report.

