#### 9.1 Randomization

Once eligibility and consent are confirmed, participants will be randomly assigned to the experimental or placebo group in a 1:1 allocation ratio, stratified by site. At 90 days the two groups will change arms and the placebo group will receive the stem cell infusion and the initially treated group will receive a LRS at a volume of 1 mL/kg.

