#### 9.2 Primary Safety Analysis

All safety outcomes will be summarized in tables and listings presented by experimental group. Continuous measures will be summarized with descriptive statistics (N, mean, SD, median, min, max). Categorical measures will be summarized using counts and percentages. The incidence of adverse events will be presented by toxicity grade, MedDRA system organ class and preferred term, and by relationship of the adverse events to the study treatment and compared using a Fisher's Exact Test. Laboratory and vital signs data will be presented using shift tables and summaries of change from baseline to the maximum post-administration value and compared using analysis of covariance (ANCOVA) models.

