#### 9.3 Efficacy Analyses

The actual score and calculated change from baseline for each outcome measure (LV end diastolic volume, LVEF, Ventricular Arrhythmias, Kansas City Cardiomyopathy Questionnaire and the New York Heart Association Classification) will be tabulated for each scheduled assessment visit. Summary statistics will consist of sample size (N), means, standard deviations, medians, and minimum and maximum values will be used to summarize the data. Subjects who receive complete dose of investigational product or LRS and have post-administration assessments will be used as the efficacy evaluable population for statistical analysis.

The primary efficacy endpoint will be evaluated and is the change from baseline to Day 90, and 180 on the above measures. For each of the efficacy endpoints, a mixed-effect repeated measures (MMRM) analysis will be conducted to determine if the change from baseline to six months in the experimental group is different than that for the placebo group. The model will include the change in endpoint score from baseline to each post-baseline visit as the outcome variable, the baseline score, time, study site, treatment group and time-by-treatment interaction as fixed effects, and participant as a random effect. An unstructured covariance matrix will be used to model the within-subject variance-covariance errors. Time (0, 30d, 90d, and 180d) will be treated as a categorical variable in the analysis. The mixed model seamlessly accommodates different times of measurement as well as missed measurement and data from participants who are lost to follow up.

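### Lung function is in the primary safety endpoint, but Section 9.2 gives it only group summaries; a baseline- and site-adjusted arm difference with a 95% CI would be a cheap, optional improvement

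*Combined protocol and SAP*

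**What the plan says.** The synopsis lists the pulmonary function test under the primary safety endpoint with the timing "Baseline and day 90 post stem cell infusion"; Section 4.2 has "Baseline and day-90 post infusion". Section 7.1 defines the measures as FEV1, percent predicted FEV1 and DLCO. Appendix A schedules spirometry and DLCO for every subject at screening, Day 90 and Day 180, so both arms have a baseline and a Day 90 value in the initial phase.

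Section 9.2 sets a general rule: "All safety outcomes will be summarized in tables and listings presented by experimental group". For continuous measures it adds: "Continuous measures will be summarized with descriptive statistics (N, mean, SD, median, min, max"). Two kinds of data get more. Adverse events are compared by Fisher's exact test. For the other kind the text is: "Laboratory and vital signs data will be presented using shift tables and summaries of change from baseline to the maximum post-administration value", followed by comparison with ANCOVA models.

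Section 9.3 promises "The actual score and calculated change from baseline for each outcome measure (LV end diastolic volume, LVEF, Ventricular Arrhythmias, Kansas City Cardiomyopathy Questionnaire" and NYHA class) at each visit, and an MMRM for the efficacy endpoints. Section 9 opens with "Statistical analyses will be descriptive" and promises a detailed SAP before data analysis. Section 9.1 randomises "in a 1:1 allocation ratio, stratified by site".

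**The concern.** A primary safety measure defined by a baseline and a Day 90 value calls for a change measure. Here it gets less than the laboratory and vital signs data, which have change from baseline and a between-group model. With about 10 subjects per arm, summaries by visit ignore each subject's own baseline, and much of the spread in lung function may be stable differences between people.

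Lung function deserves the attention because of the route of delivery. Section 2.2 says intravenous cells are at first held mainly in the lungs, and the rat study in Section 2.6 found most of them there at 1 hour. The background does not point only to harm: that study found little activity after 5 days, and the placebo-controlled intravenous MSC trial in Section 2.8.1 reported better forced expiratory volume than placebo. A fall and a gain are both of interest. What is at stake is whether the report shows how large a fall the trial can exclude, so that no visible difference is not taken to mean no effect.

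**Working it through.** **1. Which stated method applies.** Spirometry and DLCO have their own heading in Section 7.1, apart from the clinical laboratory assessments, and Section 4.2 does not list them as vital signs. The change-and-ANCOVA sentence in Section 9.2 therefore does not reach them. The list in Section 9.3 (LV end-diastolic volume, LVEF, ventricular arrhythmias, KCCQ, NYHA) does not either. Only the general descriptive rule remains.

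**2. What the planned tables allow.** Group means at baseline and Day 90 can be subtracted to give a difference in mean change if the data are complete. The SD of the change is not promised, so the tables alone give no interval for it. The only interval they support is one on raw Day 90 values. The listings would supply the paired values.

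**3. Size.** The plan has no figure to reproduce: Section 9.4 gives no power calculation, and no SD or correlation for lung function appears anywhere.

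Inputs: n = 10 per arm (Section 4.1). Assumed: equal SDs at the two visits, no treatment effect on variance, 5 subjects per site per arm, no site effect, and baseline/Day 90 correlation rho from 0.3 to 0.9. Half-widths of the 95% CI are in between-subject SDs:

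- Raw Day 90: t(0.975, 18) × √(2/10) = 2.101 × 0.447 = 0.940
- Change: 0.940 × √(2(1 − rho))
- ANCOVA on baseline: t(0.975, 17) × √0.2 × √(1 − rho²) × √(1 + 1/16)
- ANCOVA on baseline and site: t(0.975, 16) × √0.2 × √(1 − rho²) × √(1 + 1/15)

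The last factor in each ANCOVA line allows for chance baseline imbalance.

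| rho | Raw Day 90 | Change | ANCOVA, baseline | ANCOVA, baseline and site | Last column against change |
|---|---|---|---|---|---|
| 0.3 | 0.940 | 1.112 | 0.928 | 0.934 | −16% |
| 0.5 | 0.940 | 0.940 | 0.842 | 0.848 | −10% |
| 0.7 | 0.940 | 0.728 | 0.695 | 0.699 | −4% |
| 0.8 | 0.940 | 0.594 | 0.584 | 0.587 | −1% |
| 0.9 | 0.940 | 0.420 | 0.424 | 0.427 | +2% |

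Simulation (8,000 runs) agrees with the change and ANCOVA columns to within 0.003.

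At rho 0.8 to 0.9 nearly all the gain comes from using the baseline at all, and simple change does as well as ANCOVA. At rho 0.5 or below simple change is no better than raw values, or worse. ANCOVA is the safer choice when rho is unknown.

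**4. In litres.** For an unadjusted comparison of change, the half-width is 0.94 times the SD of the change. Assumed SDs of FEV1 change of 0.15, 0.20, 0.30 and 0.40 L give 0.14, 0.19, 0.28 and 0.38 L.

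**5. Other arm sizes.** With 8 evaluable per arm the multiplier is 1.07. With 15 per arm, a figure that appears in Sections 5.2 and 6.1, it is 0.75.

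**The case against.** The case for leaving the plan alone is substantial.

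- *Respiratory status is followed in other ways.* Oximetry is scheduled at every follow-up visit to Day 180, and adverse events are collected to study completion. Respiratory rate is a listed vital sign, so it already gets change from baseline and ANCOVA, and for it the highest value points the right way. This stands. A reader might infer that evidence on lasting lung effects rests on spirometry and DLCO alone; the schedule does not support that. They are the only direct lung function tests.
- *The data are reported.* Section 9.2 covers all safety outcomes in tables and listings. A reader might infer that lung function is left out or that the comparison is lost; neither is so. The gap is in what the report estimates, not in what is collected.
- *The study is descriptive and states no interval for any outcome.* ECG intervals, also in the primary safety endpoint, are treated the same way. This lowers the priority. It does not make the addition out of place: an estimate with an interval is descriptive, and Sections 9.2 and 9.3 already plan Fisher's test, ANCOVA and MMRM.
- *The SAP may supply it.* It may, but Section 9.2 already states a lesser method for this measure, and the SAP is a suitable place for the sentence.
- *The size is hypothetical.* It is: rho is assumed, no raw Day 90 test is planned, and the stopping rules in Section 8.5 do not use spirometry or DLCO.

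**Conclusion.** The gap holds on the text. Lung function is a primary safety measure with a baseline and a concurrent control at Day 90, yet its stated analysis is group description, while laboratory and vital signs data get change from baseline and ANCOVA.

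The consequence is modest. Relative to raw Day 90 values, site-adjusted ANCOVA narrows the interval by about 38% at rho 0.8 (0.587 against 0.940) and by under 1% at rho 0.3 (0.934 against 0.940). Both rest on 10 per arm and an assumed correlation. The trial remains imprecise for modest lung effects either way.

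A reader might infer that the plan overlooks a predicted lung injury. The documents do not support that: the early lodging of cells was short-lived in the rat study, and the cited intravenous trial saw improvement. This is a cheap, optional improvement, not a defect that must be corrected before the trial can be interpreted.

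**What to change.** Add to Section 9.2 or the SAP, as its own text:

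> FEV1 (or percent predicted FEV1) and DLCO will be summarised as change from baseline to Day 90 of the initial phase, with the cells-minus-LRS difference and 95% CI from an ANCOVA adjusting for baseline value and site. The Day 90 to Day 180 change will be summarised descriptively by treatment received, for DLCO where it is measured at Day 180 (Appendix A).

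- Do not extend the laboratory rule to lung function. It takes the highest value after infusion, and harm here is a fall.
- Choose one of FEV1 and percent predicted FEV1 in advance, since they are nearly redundant.
- Naming Day 90 works whether or not Day 60 tests are done; Section 7.3 lists them and Appendix A does not.
- The Day 180 condition is needed because Section 7.1 states DLCO only at screening and 90 days, while Appendix A also schedules it at Day 180.
- The second sentence also covers the synopsis timing, which for placebo-first subjects falls at about Day 180.

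Cost: one or two more tables and an interval that will be wide. No new test, visit or patient is needed.

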#### 9.3 Efficacy Analyses

The actual score and calculated change from baseline for each outcome measure (LV end diastolic volume, LVEF, Ventricular Arrhythmias, Kansas City Cardiomyopathy Questionnaire and the New York Heart Association Classification) will be tabulated for each scheduled assessment visit. Summary statistics will consist of sample size (N), means, standard deviations, medians, and minimum and maximum values will be used to summarize the data. Subjects who receive complete dose of investigational product or LRS and have post-administration assessments will be used as the efficacy evaluable population for statistical analysis.

The primary efficacy endpoint will be evaluated and is the change from baseline to Day 90, and 180 on the above measures. For each of the efficacy endpoints, a mixed-effect repeated measures (MMRM) analysis will be conducted to determine if the change from baseline to six months in the experimental group is different than that for the placebo group. The model will include the change in endpoint score from baseline to each post-baseline visit as the outcome variable, the baseline score, time, study site, treatment group and time-by-treatment interaction as fixed effects, and participant as a random effect. An unstructured covariance matrix will be used to model the within-subject variance-covariance errors. Time (0, 30d, 90d, and 180d) will be treated as a categorical variable in the analysis. The mixed model seamlessly accommodates different times of measurement as well as missed measurement and data from participants who are lost to follow up.

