## STATISTICAL METHODS

All randomized subjects who receive at least part of a dose of aMBMC or LRS will be included in the safety analysis. Subject safety data will be analyzed by actual dose level (i.e., number of cells/kg). Adverse events will be coded according to the MedDRA adverse event dictionary. The results will be tabulated to examine their frequency, affected organ systems, severity and relationship to study stem cell administration. The results of laboratory tests will be similarly evaluated. The efficacy analyses will include subjects that received the full dose of aMBMC or LRS and have the appropriate follow-up completed at the scheduled assessments (i.e., efficacy evaluable population). Safety measures include the composite of all-cause mortality, admission for worsening HF and all-cause admissions. Measurement of left ventricle end diastolic volume, left ventricle end systolic volume, left ventricular ejection fraction (LVEF), longitudinal strain and strain rate, global and segmental strain and strain rate, exercise capacity by 6 minute walk distance test, biomarkers, Kansas City Cardiomyopathy Questionnaire (KCCQ) and the New York Heart Association (NYHA) Classification will be completed in the entire efficacy evaluable population. A formal statistical analysis plan will be conducted in accordance with the guidelines of Good Clinical Practice (GCP), including the archiving of essential documents.

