#### 5.3 Subject Discontinuation and Withdrawal

Subjects may voluntarily withdraw from the study at any time. In the event of early withdrawal, the reason for withdrawal will be recorded on the appropriate CRF. Attempts to complete early termination exam as defined in 7.4 will be made. The Investigator has the right to discontinue a subject from the study for any medical reason that the investigator determines may jeopardize the subject's safety if he or she continues in the study, or for reasons of noncompliance (e.g., missed visits, use of other investigational drugs, etc.). Each site Investigator may enroll up to 3 additional subjects to each group to offset subjects that are withdrawn or terminated.

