#### 6.2 IV Administration of aMBMC or Placebo

On the day of infusion, prior to study product administration, a skin test will be administered using 0.1 mL aliquot of the Final Formulation (Appendix C).

An intravenous line will be placed into an appropriate vein on the upper extremity or hand with 0.9% sodium chloride solution running to keep the vein open. The study solution described above will be taken up in an 18-gauge needle into a 60 mL syringe with an eccentric (offset) tip. The needle will be removed and infusion tubing will be attached to the syringe. The syringe with infusion tubing will be placed in a metered dose syringe pump positioned horizontally with the syringe rotated such that the syringe tip is at the lowest position. The product will be infused intravenously into the subject's arm at a constant rate of approximately 2 mL/min. The applicable volume for the target dose will be delivered within  $\pm$  2 mL. Depending on subject's weight, up to three 60 mL syringes of product may be infused. After the entire product volume is delivered, 25 mL of LRS (without cells) will be infused at 2 mL/min to deliver cells from the infusion line for more accurate dosing. Subjects in the placebo group will receive intravenous LRS. Their syringes will be labeled as above to preserve blinding and followed by 25 mL of LRS infusion as above.

If the subject has an adverse reaction during the infusion, the infusion may be interrupted or slowed according to the severity of the reaction. All appropriate treatment will be given to reduce any discomfort and ensure the subject's safety. The infusion may be restarted, if interrupted, if the subject is not considered to be at risk by the Investigator and the subject consents.

All subjects will receive the follow-up tests and evaluations as per Appendix A.

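### The only efficacy population drops randomised subjects for post-randomisation reasons that can depend on the assigned product, and its two definitions conflict

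*Combined protocol and SAP*

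**What the plan says.** The synopsis, under Statistical Methods, limits the efficacy analyses to subjects who "received the full dose of aMBMC or LRS and have the appropriate follow-up completed at the scheduled assessments". Section 9.3 gives its own rule for the set of the same name: "Subjects who receive complete dose of investigational product or LRS and have post-administration assessments will be used as the efficacy evaluable population". It does not say how many assessments are needed, or which ones.

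Section 9.3 then plans a mixed model for repeated measures (MMRM) to test whether change from baseline differs between the experimental and placebo groups. It says this model "seamlessly accommodates different times of measurement as well as missed measurement and data from participants who are lost to follow up".

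Other sections determine who can end up without a complete dose:

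- Section 7.2.1 and Appendix A place randomisation at screening (Days 1 to 2). Section 7.2.2 places the first infusion at Day 7 ± 3.
- Section 6.2 and Appendix C require a skin test with the final formulation on the day of infusion. A positive result disqualifies the subject. Section 7.3 and Appendix A repeat the test before the Day 90 infusion.
- Section 6.2 provides that, after an adverse reaction, "the infusion may be interrupted or slowed according to the severity of the reaction". Restart is allowed under conditions.

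The safety set in the synopsis is wider: it takes any randomised subject who received some of an infusion. No efficacy analysis of all randomised subjects is planned, either as the main analysis or as a sensitivity analysis.

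**The concern.** Randomisation makes the two groups comparable as they were formed. A set chosen by what happened afterwards keeps that comparability only if the reasons for exclusion are unrelated to product or unrelated to outcome. Here the skin test and the infusion both involve the assigned product, so exclusion could differ between groups.

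The second problem is that the set is not reproducible. Two analysts following the synopsis and Section 9.3 could reach different subject counts and different LVEF results from the same 20 subjects, with no stated rule for choosing between them. At stake is the secondary endpoint, change in LVEF, and the preliminary efficacy reading that the trial is meant to give.

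**Working it through.** The plan gives no alpha, power, effect size, SD or rate of incomplete dosing, so there is no figure of its own to reproduce. The main check is to classify subjects under each definition.

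| Subject | Synopsis | Section 9.3 |
|---|---|---|
| Randomised, positive skin test before the first infusion | Out | Out |
| First infusion stopped and never completed | Out | Out |
| Both infusions complete, Day 90 image, no Day 180 image | Out on the natural reading | In |
| First infusion complete; Day 90 infusion incomplete or not given | Not defined | Not defined |
| Both infusions complete, no post-baseline image | Out on the natural reading | In if other assessments exist, but no LVEF change to analyse |

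Rows 1 and 2 are the post-randomisation exclusion, common to both definitions. Row 3 is the direct conflict: Section 9.3 counts on the model to use this subject, and the synopsis removes the subject before the model is fitted. Row 4 arises because every subject is due two infusions and neither text says whether a complete dose means the first, either or both. Row 5 shows that for LVEF the conflict is confined to subjects with some post-baseline imaging.

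**Weight of one subject.** With 10 per group, 1/10 = 10% of an arm.

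**Shift in an arm mean.** Let a fraction f be excluded, with mean change lower by d than that of the rest, whose mean is m. The full-arm mean is (1 − f)m + f(m − d) = m − fd, so exclusion moves the mean by fd. One exclusion in 10 moves it by 0.1d. The documents give neither f nor d, and d may have either sign.

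**Illustration on assumed values.** Simulation with no true effect, 10 per group, a two-sample t-test at two-sided 0.05 and exclusions from one group only. This is not the planned MMRM.

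| Excluded from one group | Strictly the worst outcomes: bias (SD) / type I error | Exclusion correlated 0.5 with outcome: bias (SD) / type I error |
|---|---|---|
| 1 | 0.17 / 0.072 | 0.09 / 0.053 |
| 2 | 0.32 / 0.115 | 0.16 / 0.065 |
| 3 | 0.46 / 0.165 | 0.23 / 0.075 |

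With nobody excluded, the simulated type I error is 0.048. The direction is set by the assumption that poor outcomes are the ones removed. If exclusion were unrelated to outcome, it would cost precision but add no bias.

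**The case against.** The strongest reply is that this is an exploratory trial of 20. Efficacy is secondary, Section 9 calls the analyses descriptive, Section 9.4 disclaims power, and a detailed analysis plan is still to be written. An evaluable set is a common choice in such a trial. This limits the consequence, but Section 9.3 still plans a between-group test.

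The synopsis wording can also be read measure by measure, as the follow-up needed for each outcome; Section 9 supports that by basing analyses on available data. On that reading the conflict narrows. The need for one clear definition remains, as does the exclusion of incompletely dosed subjects.

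Three stronger readings are tempting, and the documents do not support them.

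- A reader might infer that the exclusions favour cells. An interrupted infusion may be restarted and finished, and nothing links infusion reactions to LVEF. Section 2.7 reports one mild, possibly related event in a 15-patient stroke study and no SAEs in 19 treated STEMI patients; it describes no incomplete infusions.
- A reader might infer from Section 5.3 that subjects outside the efficacy set are replaced by better tolerators. Each site "may enroll up to 3 additional subjects to each group to offset subjects that are withdrawn or terminated", which does not cover a partially dosed subject who stays in follow-up. The allowance caps enrolment and does not measure bias.
- Section 9 says "Tables will summarize all safety and efficacy outcome measures by actual treatment received". A reader might take this as abandoning the randomised comparison. It governs tables, and in a crossover it is a natural way to label periods. The MMRM uses a treatment-group term that is not further defined.

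**Conclusion.** The point holds. Both definitions remove randomised subjects for events that follow randomisation and can depend on the assigned product. They disagree about fully dosed subjects with partial follow-up, and neither says which infusion must be complete. No all-randomised efficacy analysis stands beside them.

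The direction and size of any bias cannot be determined from the documents. What is certain is the leverage: one exclusion is 10% of an arm of 10. The simulated range, from almost no inflation of type I error (0.053) to 0.165, depends wholly on the assumed number of exclusions and their link to outcome. The matter should be settled before data analysis, but it does not affect the primary safety objective.

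**What to change.** 1. Write one definition and use it in both the synopsis and Section 9.3.
2. Make the main efficacy set all randomised subjects, analysed by randomised sequence, with every available post-baseline value in the MMRM.
3. Report by group the number randomised but not infused, including those disqualified by the skin test. Reusing the safety set for efficacy would not be enough, because it omits these subjects.
4. Keep the full-dose evaluable set as a sensitivity analysis, and state whether it refers to the first, either or both infusions.
5. Keep the data of any replaced subject in the main set.

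This changes who is counted. It leaves the infusion and skin-test rules as they are.

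The cost is protocol and analysis-plan wording, plus slight dilution of the effect from partial doses. No new visits are needed: Section 6.2 gives all subjects the Appendix A follow-up, and the early termination visit in Section 7.4 includes MRI and echocardiography. A subject with no post-baseline value still adds nothing to the model, which is why the counts in item 3 matter.

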## SECONDARY ENDPOINT

#### Efficacy

Change in LVEF from baseline to day 90 post initial infusion. After the crossover phase all patients will be evaluated for change from the new baseline (day 90 after the initial phase) to day 90 post new infusion.

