## SECONDARY ENDPOINT

## Efficacy

Change in LVEF from baseline to day 90 post-initial infusion. After the crossover phase all patients will be evaluated for change from the new baseline (day 90 after the initial phase) to day 90 post new infusion

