## EXPLORATORY ENDPOINTS

Changes between baseline and days 90 post-initial infusion. After the crossover phase all patients will be evaluated for changes from the new baseline (day 90 after the initial phase) to day 90 post new infusion. MRI

- 5. Left ventricular end systolic volume index
- 6. Wall motion segmental score
- 7. LV end-systolic and end-diastolic dimensions
- 8. T2 MRI imaging

Changes between baseline and days 90 post-initial infusion. After the crossover phase all patients will be evaluated for changes from the new baseline (day 90 after the initial phase) to day 90 post new infusion. Echocardiogram

- 4. Changes in LV mechanics by speckle-tracking echocardiography (longitudinal and circumferential strain and strain rate)
- 5. Estimated systolic pulmonary artery pressures
- 6. Changes in MR severity (most patients have mild to moderate MR).

Changes between baseline and days 30, 60, and 90 post-initial infusion. After the crossover phase all patients will be evaluated for changes from the new baseline (day 90 after the initial phase) to day 30 and 90 post new infusion.

Exercise capacity

6 minute walk distance

Health status

- a. New York Heart Association Class (NYHA) class
- b. Kansas City Cardiomyopathy Questionnaire

Heart failure status

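### Section 9.3 makes five measures at two times the primary efficacy endpoint, while the synopsis and Section 4.2 name LVEF alone and rank it secondary

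*Combined protocol and SAP*

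**What the plan says.** Section 9.3 lists its outcomes as "LV end diastolic volume, LVEF, Ventricular Arrhythmias, Kansas City Cardiomyopathy Questionnaire and the New York Heart Association Classification" and then states: "The primary efficacy endpoint will be evaluated and is the change from baseline to Day 90, and 180 on the above measures". It fits a mixed model for repeated measures to each efficacy endpoint and asks whether the change to six months differs between the experimental and placebo groups. It gives no significance level, testing order or multiplicity adjustment.

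The endpoint sections say something else. Under the secondary endpoint heading, the synopsis has "Change in LVEF from baseline to day 90 post initial infusion" and Section 4.2 has "Change in LVEF from baseline to day 90 post-initial infusion". For the second period, Section 4.2 has patients "evaluated for change from the new baseline (day 90 after the initial phase) to day 90 post new infusion". The exploratory list in 4.2 holds the "Kansas City Cardiomyopathy Questionnaire", NYHA class and "Left ventricular end systolic volume index". Clinical arrhythmias appear in 4.2 under the primary safety endpoint. LV end-diastolic volume appears in neither endpoint list.

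On the status of the analysis, Section 9 opens with "Statistical analyses will be descriptive" and promises a detailed SAP before data analysis. Section 9.4 calls the study exploratory and says that power did not determine its size.

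**The concern.** Sections 4.2 and 9.3 disagree on the rank of the efficacy endpoint, on how many measures it contains, on which ones they are, and on how the second period is measured. Nothing says which section governs. Section 4.2 has no primary efficacy endpoint at all, so 9.3 creates a tier that the rest of the protocol lacks and fills it with one secondary, two exploratory, one safety and one unlisted measure.

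At stake is which efficacy result the report leads with. Someone following 9.3 could put any of the five measures first and call it primary; someone following 4.2 could put only LVEF first. With 10 subjects per group, a chance result on one of several measures is easily over-read.

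**Working it through.** **1. The two lists side by side**

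| Measure | Section 9.3 | Section 4.2 |
|---|---|---|
| LVEF | part of the primary efficacy endpoint | secondary; the one efficacy endpoint at that rank |
| KCCQ | part of the primary efficacy endpoint | exploratory |
| NYHA class | part of the primary efficacy endpoint | exploratory |
| Ventricular arrhythmias | part of the primary efficacy endpoint | clinical arrhythmias are a primary safety item |
| LV end-diastolic volume | part of the primary efficacy endpoint | not listed (end-diastolic dimension is, as exploratory) |
| LVESV index, 6-minute walk, biomarkers | not listed | exploratory |

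The MRI text in Section 7.1 gives a third list (both LV volumes, LVEF and T2 images), which matches neither.

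**2. The times**

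Both sections include the change from baseline to day 90 after the first infusion. They part in the second period: 4.2 starts again from a new baseline at day 90, and 9.3 measures Day 180 from baseline.

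By Day 180 one group has had cells then Lactated Ringer's, and the other has had Lactated Ringer's then cells (Sections 4.1 and 9.1). Write e(t) for the effect of cells t days after they are given, and assume the same background trend in both groups. The difference between groups in change from original baseline to Day 180 is then

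(trend + e(180)) − (trend + e(90)) = e(180) − e(90).

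This compares an older dose with a newer one, and is zero if the effect at 90 days persists to 180. It is not a cells-versus-placebo contrast.

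**3. How many tests**

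- Named in 9.3: one six-month contrast for each of 5 measures = 5.
- If the Day 90 results are tested as well: 5 × 2 = 10.
- Under 4.2: LVEF once = 1, or LVEF in each of two periods = 2.

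**4. Chance of at least one false positive**

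The documents state no significance level, so there is no figure of the plan's own to reproduce. I assume α = 0.05 two-sided and show 0.025 and 0.10. If the tests are independent, the chance is 1 − (1 − α)^k:

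| k | α = 0.025 | α = 0.05 | α = 0.10 |
|---|---|---|---|
| 1 | 0.025 | 0.05 | 0.10 |
| 2 | 0.049 | 1 − 0.95² = 0.0975 | 0.19 |
| 5 | 0.119 | 1 − 0.95⁵ = 0.226 | 0.41 |
| 10 | 0.224 | 1 − 0.95¹⁰ = 0.401 | 0.65 |

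The measures will be correlated, by an amount the documents do not give. A simulation of equally correlated normal test statistics (200,000 draws, α = 0.05) gives:

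| k | r = 0.3 | r = 0.5 | r = 0.7 | r = 0.9 |
|---|---|---|---|---|
| 5 | 0.21 | 0.18 | 0.15 | 0.10 |
| 10 | 0.35 | 0.29 | 0.21 | 0.13 |

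With a five-by-two structure (correlation 0 to 0.5 between measures, 0.3 to 0.7 between times), ten tests give 0.29 to 0.39.

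**The case against.** The strongest reply is that this is a small safety trial. Its primary objective and endpoint are safety, its title promises only preliminary efficacy, Section 9 calls the analyses descriptive, Section 9.4 disclaims power, and a detailed SAP is to follow. All of that stands, and it means that no stated error rate is breached. It does not remove the conflict. Section 9.3 still uses the word primary and still tests every measure between groups, which itself sits badly with the descriptive statement. The promised SAP is not in these documents, and its author would inherit two lists with no rule for choosing between them.

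A reader might also infer stronger points that the documents do not support:

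- **That ten tests and a 40% error rate are planned.** Section 9.3 names only the six-month contrast for its models. The Day 90 results are part of the endpoint definition and can be estimated from the model, but no Day 90 test is named. The 40% figure also needs independence.
- **That the alternative carries exactly 5%.** That holds for one LVEF contrast. Section 4.2 evaluates LVEF in two periods, and testing both separately gives 9.75% if independent.
- **That the LVEF method is left open.** Section 7.1 counts LVEF among the efficacy endpoints assessed by MRI, the MRI reading is central and blinded, and the echocardiography list in 4.2 does not contain LVEF. Because 7.1 also derives LVEF from echocardiography, naming MRI in 4.2 and 9.3 is worthwhile tidying, but no more.
- **That measures missing from 9.3 go unreported.** The synopsis statistical methods include end-systolic volume, 6-minute walk and biomarkers, and Section 9 promises tables for all outcome measures. The lack of a model for exploratory measures is no defect here.
- **That a nominally positive result would be uninterpretable.** It would be hypothesis-generating, as the exploratory label implies.

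**Conclusion.** The point holds as an internal contradiction that should be reconciled. Section 9.3 conflicts with the synopsis and Section 4.2 on rank, content and timing, and its Day 180 change does not compare cells with placebo. Under the assumed two-sided 5% level and no true effect, following 9.3 raises the chance of at least one false positive from 5% to about 23% for the five named tests if independent, or 10% to 21% at correlations of 0.9 to 0.3. If the Day 90 results were also tested, it would be 40% under independence. These figures measure the room for selection in an exploratory trial; they are not a breach of a stated error rate. The contradiction itself rests on the text alone and needs no assumption about the level or the correlations.

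**What to change.** In Section 9.3:

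1. Remove the primary efficacy endpoint label. State that the efficacy endpoint is the secondary endpoint of 4.2: change in LVEF, read by the blinded MRI core laboratory, from baseline to day 90 after the initial infusion, cells versus placebo.
2. Measure the second-period LVEF change from the new day-90 baseline, as in 4.2, and report it as supportive. Drop the Day 180 change from original baseline as a cells-versus-placebo contrast.
3. Limit testing to the single LVEF contrast in step 1, in place of a test for every efficacy endpoint. Report all other 4.2 efficacy measures as exploratory estimates with 95% confidence intervals and no significance claims.
4. Move ventricular arrhythmias to the safety analysis.
5. Make the 9.3 list match 4.2 in full. Either add LV end-diastolic volume to 4.2 as exploratory or take it out of 9.3.
6. Name MRI as the LVEF method in 4.2 as well, with echocardiographic LVEF as supportive only.

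The cost is protocol and SAP wording and a few more descriptive tables, with no added visits or subjects. The sponsor gives up significance claims on the other measures.
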